4. ANALYSIS POPULATIONS

4.1. All Enrolled Population

The all enrolled population will include all subjects with a non-missing date of informed consent. The all enrolled population will be utilized for disposition summaries.

4.2. Run-in Period Population

The run-in period population will include all enrolled subjects who are not screen failures and enter the Run-in period. The run-in period population will be presented in disposition summaries.

4.3. Intent-to-Treat Population

The intent-to-treat (ITT) population will include all subjects who are randomized and receive at least 1 dose of study treatment, with subjects grouped according to randomized treatment. The ITT population will be utilized for efficacy analyses.

4.4. Safety Population

The safety population will include all subjects who receive at least 1 dose of study treatment, with subjects grouped according to their actual treatment. If GB001 was taken, based on kit and study treatment accountability data, subjects will be included in the GB001 40 mg group. The safety population will be utilized for safety and PK analyses.

5. STUDY PATIENTS

5.1. Disposition of Patients

The disposition of subjects will be summarized for the all enrolled population. The number and percent of subjects who are screened, screen failures, run-in period participants, completed run-in period, run-in period failures, and randomized in error, along with screen failure reasons, run-in period failure reasons, reasons not randomized, and eligibility or randomization criteria not met will be summarized overall. In addition, the number and percent of subjects who are randomized, treated, completed study treatment, discontinued study treatment, completed the study, and withdrew from the study, along with associated reasons, and in each analysis population, will be summarized by treatment group and overall.

Disposition data will also be presented in a by-subject data listing. In addition, a listing of the randomization scheme will be presented.

5.2. Protocol Deviations

Protocol deviations will be identified and reviewed on an ongoing basis by the study team and entered into a Clinical Trial Management System. Significant protocol deviations are defined as those that can affect efficacy and/or safety assessments, the safety or mental integrity of a subject, or the scientific value of the study. Protocol deviations will be classified as significant or non-significant and will be assigned a protocol deviation type prior to unblinding. The number and percent of subjects with at least 1 significant protocol deviation overall and for each protocol deviation type will be summarized for the ITT population. In addition, COVID-19 related and non-COVID-19 related significant protocol deviations will be summarized.

Protocol deviations will also be presented in a by-subject data listing. In addition, subjects who were randomized in error and subjects who were mis-stratified based on the presence or absence of NP (CRSwNP and CRSsNP) or on the presence or absence of comorbid asthma among CRSwNP subjects at randomization will be presented in a by-subject data listing.

6. DEMOGRAPHIC AND OTHER BASELINE CHARACTERISTICS

6.1. Demographic Characteristics

Demographic characteristics will be summarized for the ITT population for the following parameters:

- Age (years; continuous [cts]; ≥ 18 -< 50, ≥ 50 -< 65, ≥ 65)
- Sex (male, female)
- Race (White, Black or African American, American Indian or Alaska Native, Native Hawaiian or Other Pacific Islander, Asian, Other)
- Ethnicity (Hispanic or Latino, Not Hispanic or Latino, Not Reported)
- Height (cm; cts)
- Weight (kg; cts)
- Body mass index (BMI [kg/m^2 ; cts; < 18.5, ≥ 18.5 -< 25, ≥ 25 -< 30, ≥ 30])
- Country (Czech Republic, Ukraine, United States)
- Region (United States, Eastern Europe [Czech Republic, Ukraine])

Demographic characteristics will also be presented in a by-subject data listing.

6.2. Baseline Disease Characteristics

Baseline disease characteristics will be summarized for the ITT population for the following parameters:

- Disease status strata at randomization and actual (CRSwNP [overall, with comorbid asthma, without comorbid asthma], CRSsNP)
- CRS/NP Surgical History
 - Any prior surgery (cts)
 - Prior functional endoscopic sinus surgery (number of surgeries and years since most recent surgery; cts; 0, 1, 2, ≥ 3 for number of surgeries)
 - Prior NP surgery (number of surgeries and years since most recent surgery; cts; 0, 1, 2, ≥ 3 for number of surgeries)
 - Prior stent placement (number of surgeries and years since most recent surgery; cts; 0, 1, ≥ 2 for number of surgeries)
 - Prior nasal septum surgery (number of surgeries and years since most recent surgery; cts; 0, 1, ≥ 2 for number of surgeries)
 - Prior rhinoplasty surgery (number of surgeries and years since most recent surgery; cts; 0, ≥ 1 for number of surgeries)

- CRS/NP History
 - CRS duration (years; cts)
 - History of NP (never had, ongoing, past; NP duration for CRSwNP subjects [years; cts])
 - Comorbid asthma (yes, no)
 - Fungal sinusitis current or prior history (yes, no)
 - Inadequate response to vaccines (yes, no)
 - Nasal blockade/obstruction/congestion (yes, no)
 - Nasal discharge (yes, no)
 - Reduction or loss of smell (yes, no)
 - Facial pain/pressure (yes, no)
 - Loss of sleep (yes, no)
 - Sinus CT scan in past 2 years (yes, no)
 - Sinus X-ray in past 2 years (yes, no)
 - Prior anti-fungal treatment (yes, no)
 - Prior saline nasal irrigations (yes, no)
 - Chronic antibiotic use in the past (yes, no)
 - Chronic antibiotic use currently (yes, no)
- Polyps present (based on visual exam by investigator) in right/left nostril for CRSwNP subjects (yes, no)
- Smoking history (never, former, current; cigarette pack-years for former and current smokers)
- Alcohol history (never, former, current)

Baseline disease characteristics will also be presented in by-subject data listings.

6.3. Atopic/Allergic Conditions

Atopic/allergic conditions will be summarized for the ITT population for the following parameters:

- Chronic Rhinosinusitis, Asthma, Seasonal Allergic Rhinitis, Perennial Allergic Rhinitis, Chronic Spontaneous Urticaria, Eosinophilic granulomatosis with polyangiitis (Churg Strauss Syndrome) (none, ongoing, past)

Atopic/allergic conditions will also be presented in a by-subject data listing.

6.4. Efficacy-Related Baseline Characteristics

Efficacy-related baseline characteristics will be summarized for the ITT population for the following parameters:

- SNOT-22 total score and 5 domain (Nasal, Ear, Sleep, General and Practical, and Emotional) scores (cts; \leq Median, $>$ Median of ITT population for total score)
- Bilateral Endoscopic NPS at Screening for CRSwNP subjects (cts; 4, 5 - 6, 7 - 8)
- Bilateral Endoscopic NPS at Baseline for CRSwNP subjects (cts; \leq 4, 5 - 6, 7 - 8)
- TSS (AM, PM; cts; \leq Median, $>$ Median of ITT population for AM TSS)
- NC score (AM, PM; cts; \leq Median, $>$ Median of ITT population for AM NC)
- Anterior rhinorrhea score (AM, PM; cts)
- Posterior rhinorrhea score (AM, PM; cts)
- Loss of sense of smell score (AM, PM; cts)
- UPSIT score (cts; Anosmia = 0 – 18, Severe Microsmia = 19 – 25, Moderate Microsmia = 26 – 30, Mild Microsmia = 31 – 34, Normal = 35 – 40)
- VAS score (cts; mild, moderate, severe, using categories defined in [Section 8.3.3.1](#))
- Lund-Mackay score (cts)
- Volume of the air (mL; cts)
- Volume of mucosa (mL; cts)
- Percentage of maxillary sinus volume occupied by disease on CT scan (cts)
- Thickness of lateral wall (mm; cts)
- ACQ-5 score for asthma subjects (cts; $<$ 1.5, \geq 1.5)

Efficacy-related baseline characteristics will also be presented in a by-subject data listing.

6.5. Biomarker Baseline Characteristics

Biomarker baseline characteristics will be summarized for the ITT population for the following parameters:

- Blood eosinophils at Screening ($10^9/L$; cts; <0.25 , ≥ 0.25)
- Blood eosinophils at Baseline ($10^9/L$; cts; <0.25 , ≥ 0.25)
- Screening and Baseline blood eosinophils ($10^9/L$; ≥ 0.25 and < 0.25)
- Maximum blood eosinophils value prior to randomization visit for CRSsNP subjects ($10^9/L$; cts; ≥ 0.25 , ≥ 0.30 , ≥ 1.50)
- Fractional exhaled nitric oxide (FeNO) at Baseline (ppb; cts; < 25 , ≥ 25)

- Chloride at Baseline (mmol/L; cts; \leq Quartile 1, $>$ Quartile 1 - \leq Quartile 2, $>$ Quartile 2 - \leq Quartile 3, $>$ Quartile 3, where quartiles are based on the ITT population)

Biomarker baseline characteristics will also be presented in a by-subject data listing.

6.6. Medical History

Verbatim targeted and general medical history terms will be coded to a SOC and PT using the Medical Dictionary for Regulatory Activities (MedDRA) Version 21.0 or later. Counting will be at the subject level for each level of summarization (e.g., any medical history, SOC, and PT), with subjects experiencing more than one occurrence of a SOC or PT counted only once. Ongoing and past medical history will be summarized for the ITT population.

Medical history will also be presented in a by-subject data listing.

6.7. Prior Medications

Verbatim prior medication terms will be coded to a drug class (anatomical therapeutic chemical [ATC2]) and PT using World Health Organization (WHO)Drug Global B3 March 2018 or later. Prior medications are defined as all medications that started prior to the date of first dose of study treatment. In general, if it is not clear whether a medication is prior due to missing or incomplete medication start date, the medication will be considered to be prior unless the non-missing portions of the start date indicate otherwise. Counting will be at the subject level for each level of summarization (e.g., any medication, ATC2, and PT), with subjects receiving more than one medication counted only once.

Prior medications will be summarized for the safety population.

In addition, MFNS use prior to informed consent, MFNS use between screening and randomization, prior ICS use overall and separately for between screening and randomization, further broken down by ICS alone and ICS + long-acting beta-agonist (LABA) and/or long-acting muscarinic antagonist (LAMA), and prior systemic corticosteroid use will be summarized for the ITT population.

6.8. Concomitant Medications

Verbatim concomitant medication terms will be coded to a drug class (ATC2) and PT using WHODrug Global B3 March 2018 or later.

Concomitant medications are defined as all medications that started on or after the date of first dose of study treatment or that started prior to the date of first dose of study treatment and stopped on or after the date of first dose of study treatment or were ongoing. In general, if it is not clear whether a medication is concomitant due to missing or incomplete medication start

and/or end dates, the medication will be considered to be concomitant unless the non-missing portions of the start and end dates indicate otherwise.

A medication may be considered as both prior and concomitant, i.e. prior and concomitant medications are not mutually exclusive. Counting will be at the subject level for each level of summarization (e.g., any medication, ATC2, and PT), with subjects receiving more than one medication counted only once.

Concomitant medications will be summarized for the safety population. In addition, concomitant MFNS use will be summarized for the ITT population.

Prior and concomitant medications will also be presented in a by-subject data listing and will include an indicator, identifying each medication as prior and/or concomitant.

Concurrent procedures will be presented in a by-subject data listing.

7. EXTENT OF EXPOSURE, COMPLIANCE, AND TIME ON STUDY

7.1. Extent of Exposure

Duration of study treatment (days, weeks, and subject-years) will be summarized for the safety population using descriptive statistics and categorically (every 4 weeks). Duration of study treatment will also be presented in a by-subject data listing.

7.2. Compliance

Compliance with study treatment will be assessed using the following formula:

Treatment compliance (%) = (# of actual tablets taken/# of expected tablets) x 100,
where # of actual tablets taken = (# of tablets dispensed - # of tablets returned) and # of expected tablets is based on actual duration of study treatment

Compliance will be summarized for the safety population using descriptive statistics and categorically (< 80, \geq 80-100, > 100-< 120, \geq 120).

Compliance with study treatment will also be presented in a by-subject data listing. In addition, IP accountability including kit information will be presented in a by-subject data listing.

7.3. Time on Study

Time on study (days and weeks, and subject-years) will be summarized for the safety population using descriptive statistics and categorically (every 4 weeks). The latest assessment date for each subject will be used in the calculation of time on study. Time on study will also be presented in a by-subject data listing.

8. EFFICACY EVALUATION

8.1. Overview of Efficacy Analysis Issues

8.1.1. Handling of Dropouts or Missing Data

A variety of methodological approaches will be applied for handling subjects with missing data; full details are provided in [Section 8.3](#).

8.1.2. Multicenter Studies

Data from all countries and sites will be pooled for the purpose of analyses.

8.2. Efficacy Endpoints

[Table 1](#) provides a summary of the statistical models/methods of primary and sensitivity analyses to be used for the primary, secondary, and select exploratory endpoints. For all efficacy analyses, disease status stratification factor values used for randomization (CRSwNP with comorbid asthma, CRSwNP without comorbid asthma, and CRSsNP) and region (United States, Eastern Europe) will be used as covariates and results will be summarized for the ITT population, unless otherwise stated.

Table 1: Efficacy Endpoints and Analysis Methods

Efficacy Endpoints	Missing Data Threshold ^a	MMRM		ANCOVA		Cox Proportional Hazards	Negative Binomial Regression ^b	Logistic Regression
		without MI	with MI	without MI	with MI			
Primary Change from baseline to Week 16 in SNOT-22 total score	< 10%	P		S				
	≥ 10%	S	P		S			
Secondary								
Change from baseline to Week 16 in Lund-Mackay score	< 10%			P				
	≥ 10%			S	P			
Change from baseline to Week 16 in NPS ^c	< 10%	P		S				
	≥ 10%	S	P		S			
Time to first response (≥ 1 point improvement from baseline) in NPS ^c						P		
Change from baseline to Week 16 in AM NC score	< 10%	P		S				
	≥ 10%	S	P		S			
Change from baseline to Week 16 in AM TSS	< 10%	P		S				
	≥ 10%	S	P		S			
Change from baseline to Week 16 in UPSIT score	< 10%			P				
	≥ 10%			S	P			
Time to first CRS exacerbation						P		
Exploratory								
Change from baseline to Week 16 in VAS score				P				
Annualized rate of CRS exacerbations							P	
Change from baseline to Week 16 in percentage of maxillary sinus volume occupied by disease on CT scan				P				

Efficacy Endpoints	Missing Data Threshold ^a	MMRM		ANCOVA		Cox Proportional Hazards	Negative Binomial Regression ^b	Logistic Regression
		without MI	with MI	without MI	with MI			
Proportion of subjects with antibiotic use due to worsening CRS by Week 16								P
Change from baseline to Week 16 in FeNO and nNO				P				
Percent change from baseline to Week 16 in FeNO and nNO				P				
Additional								
Change from baseline in SNOT-22 total score including all data	< 10%	P						
	≥ 10%		P					
Proportion of subjects with a ≥ 9 point decrease from baseline at Week 16 in SNOT-22 total score								P
Change from baseline in Lund-Mackay score including all data	< 10%			P				
	≥ 10%				P			
Change from baseline in NPS ^c including all data	< 10%	P						
	≥ 10%		P					
Proportion of subjects with a reduction from baseline of ≥ 1 in NPS ^c at Weeks 8 and 16								P
Change from baseline to Week 16 in PM NC score		P						
Change from baseline to Week 16 in PM TSS		P						

Efficacy Endpoints	Missing Data Threshold ^a	MMRM		ANCOVA		Cox Proportional Hazards	Negative Binomial Regression ^b	Logistic Regression
		without MI	with MI	without MI	with MI			
Change from baseline to Week 16 in AM and PM anterior rhinorrhea, posterior rhinorrhea, and loss of sense of smell scores		P						
Change from baseline to Week 16 in volume of the air, volume of mucosa, and thickness of lateral wall				P				
Change from baseline to Week 16 in ACQ-5 score				P				

ACQ-5 = asthma control questionnaire; AM = morning; ANCOVA = analysis of covariance; CRS = chronic rhinosinusitis; CRSwNP = chronic rhinosinusitis with nasal polyps; CT = computed tomography; FeNO = fractional exhaled nitric oxide; ITT = intent-to-treat; MMRM = mixed-effects model with repeated measures; MI = multiple imputation; NC = nasal congestion; nNO = nasal nitric oxide; NPS = nasal polyp score; P = primary; PM = evening; S = sensitivity; SNOT-22 = Sino-Nasal Outcome Test; TSS = total symptom score; UPSIT = University of Pennsylvania Smell Identification Test; VAS = visual analog scale

^a The analysis approach depends on the amount of missing data for the endpoint in the ITT population.

^b If the distribution of severe exacerbation data is underdispersed, or if the negative binomial regression model fails to converge, a Poisson regression model will be used instead.

^c Assessed in subjects in the randomized CRSwNP stratum.

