8.3.1.5. Additional Analyses of the Primary Endpoint

The proportion of subjects with a ≥ 9 point decrease from baseline at Week 16 in SNOT-22 total score will be analyzed in the subset of the ITT population who have a non-missing baseline and at least one post-baseline value. Logistic regression modeling will be used to compare the

GB001 40 mg group with placebo using as observed data with covariates for treatment group, disease status stratification factor values used for randomization (CRSwNP with comorbid asthma, CRSwNP without comorbid asthma, and CRSsNP), region (United States, Eastern Europe), and baseline SNOT-22 total score.

The number and proportion of subjects with a ≥ 9 point decrease from baseline at Week 16 in SNOT-22 total score and corresponding 95% Wilson (Score) CIs ([Wilson, 1927](#)) will be summarized by treatment group. The OR, corresponding asymptotic 95% CI along with the absolute difference in proportions and corresponding 95% CI, and p-value will be summarized for the GB001 40 mg group versus placebo. The 95% CI for the absolute difference will be Newcombe continuity-corrected CI ([Newcombe, 1998](#)). The percentage reduction in odds and corresponding 95% CI will also be provided.

The number and proportion of subjects with a ≥ 9 point decrease from baseline in SNOT-22 total score will also be summarized by visit as described above at Week 16.

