8.3.2.2. Time to Event Endpoints

Time to first response in NPS is defined as the time from the date of the first dose of study treatment to the first date with ≥ 1 point improvement in NPS from baseline for subjects in the randomized CRSwNP stratum. Subjects in the randomized CRSwNP stratum who do not experience ≥ 1 point improvement in NPS from baseline will be censored at their last post-baseline NPS assessment, or on Day 1 if no baseline NPS assessment or no post-baseline NPS assessment was performed.

CRS exacerbation is defined as deterioration of CRS symptoms requiring treatment with an antibiotic, an anti-inflammatory drug, or a symptom reliever; an Emergency Department visit; or hospitalization (Kuiper, 2018). Time to first CRS exacerbation is defined as the time from the date of the first dose of study treatment to the first date of treatment with an antibiotic, an anti-inflammatory drug, or a symptom reliever, the date of Emergency Department visit, or the date of hospitalization, whichever occurs first. Subjects without a CRS exacerbation will be censored at their last post-baseline CRS exacerbation assessment, or on Day 1 if no post-baseline CRS exacerbation assessment was performed.

For the primary analysis of both time to event endpoints, all data through Week 16 will be included; a sensitivity analysis of both time to event endpoints will be performed including all data.

The number and proportion of subjects with a response in NPS will be summarized for subjects in the randomized CRSwNP stratum. Time to first response in NPS will be compared between treatment groups using a Cox proportional hazards model and will include covariates for treatment group, disease status stratification factor values used for randomization (CRSwNP with comorbid asthma, CRSwNP without comorbid asthma, and CRSsNP), region (United States, Eastern Europe), and baseline NPS.

The number and proportion of subjects with CRS exacerbations will be summarized. Time to first CRS exacerbation will be analyzed using a Cox proportional hazards model and will include covariates for treatment group, disease status stratification factor values used for randomization (CRSwNP with comorbid asthma, CRSwNP without comorbid asthma, and CRSsNP), and region (United States, Eastern Europe).

The exact method will be used to handle ties in event times.

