8.3.3.4. Proportion of Subjects with Antibiotic Use Due to Worsening CRS by Week 16

The proportion of subjects with antibiotic use due to worsening of CRS by Week 16 will be analyzed using a logistic regression model to compare the GB001 40 mg group with placebo, using the approach described in [Section 8.3.1.5](#), excluding baseline SNOT-22 total score as a covariate in the model.

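### The exploratory antibiotic-use endpoint is analysed by logistic regression with no allowance for incomplete follow-up and no stated coding for subjects who withdraw before Week 16 without antibiotics

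*SAP*

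**What the plan says.** In SAP Table 1 (Section 8.2) the row "Proportion of subjects with antibiotic use due to worsening CRS by Week 16" carries a single entry, primary under logistic regression. It has no missing-data threshold and no sensitivity analysis.

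SAP 8.3.3.4 says: "The proportion of subjects with antibiotic use due to worsening of CRS by Week 16 will be analyzed using a logistic regression model". It refers to 8.3.1.5 for the method and makes one change to it, "excluding baseline SNOT-22 total score as a covariate in the model".

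SAP 8.3.1.5 was written for a SNOT-22 responder at Week 16. It analyses that outcome "in the subset of the ITT population who have a non-missing baseline and at least one post-baseline value" and compares the "GB001 40 mg group with placebo using as observed data with covariates for treatment group", so there is no imputation.

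SAP 8.1.1 refers missing-data handling to Section 8.3, but Section 8.3 gives no rule for this endpoint.

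The related exacerbation endpoints do account for follow-up. In SAP 8.3.2.2, "Time to first CRS exacerbation will be analyzed using a Cox proportional hazards model", with event-free subjects censored at their last exacerbation assessment and Kaplan-Meier summaries alongside. In SAP 8.3.3.3 the exacerbation rate model has log follow-up time as an offset.

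**The concern.** A SNOT-22 response is measured at a visit. Antibiotic use by Week 16 accumulates over time and has no baseline value. A yes is known as soon as it happens, whereas a no is fully known only if the subject is followed to Week 16. An approach built for the first kind of outcome leaves open what to do with a subject who leaves at, say, Week 3 without an antibiotic.

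That subject has post-baseline data, so an as-observed analysis would most naturally record no antibiotic use and understate the 16-week risk. Leaving the subject out, while keeping users who later withdraw, retains early events and discards early non-events, which overstates the risk. If withdrawal is unequal, the odds ratio departs from 1 with no drug effect, in a direction set by a coding choice that the SAP does not record.

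**Working it through.** **The plan's own figures.** The documents state no risk, power or precision for this endpoint. The only usable input is the overall 15% dropout assumed in SAP 2.5 and Protocol 9.2. The sample-size statement that contains it reproduces: 50 × 0.85 = 42.5 per arm, difference 12.0 and SD 16.8 give power 0.902 by the noncentral t, against a stated 90% or so.

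**Assumptions, not from the documents.** No treatment effect; true 16-week risk h = 0.25 in both arms; constant event hazard; a fraction d withdraws at times uniform over 16 weeks, independently of events.

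**Formulas.**
- λ = −ln(1 − h) = −ln(0.75) = 0.2877.
- Mean probability of an event before withdrawal, among withdrawers: pe = 1 − h/λ = 1 − 0.25/0.2877 = 0.131.
- Coding A, event-free withdrawers counted as non-users: p = (1 − d)h + d·pe.
- Coding B, event-free withdrawers removed but users kept: p = [(1 − d)h + d·pe] / [(1 − d) + d·pe].
- Coding C, all withdrawers removed, users included: p = (1 − d)h / (1 − d) = h.

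**Equal dropout, d = 0.15.**
- A: 0.85 × 0.25 + 0.15 × 0.131 = 0.232.
- B: 0.232 / (0.85 + 0.0196) = 0.267.
- C: 0.250.

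The odds ratio is 1.00 under all three, but A and B misstate the proportion in both arms.

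**Unequal dropout, GB001 versus placebo.**

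| Dropout | A: proportions | A: OR | B: proportions | B: OR |
|---|---|---|---|---|
| 20% vs 10% | 0.226 vs 0.238 | 0.94 | 0.274 vs 0.261 | 1.07 |
| 25% vs 5% | 0.220 vs 0.244 | 0.87 | 0.281 vs 0.255 | 1.14 |

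Coding C gives 1.00 throughout.

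**Check with another dropout model.** With competing constant hazards of first antibiotic use (a) and withdrawal (g), the observed proportion under A is a/(a + g) × [1 − exp(−(a + g))]. For true risks of 10% to 40%:
- 20% vs 10% dropout: OR 0.92–0.94 (A) or 1.06–1.07 (B).
- 25% vs 5% dropout: OR 0.85–0.88 (A) or 1.13–1.14 (B).

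Timing matters. If all withdrawals came immediately after randomization, coding A at 20% risk and 25% vs 5% dropout would give 0.15 vs 0.19, OR 0.75.

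**Against the precision available.** At 25% risk and 50 per arm, SE(log OR) ≈ √[2/(50 × 0.25 × 0.75)] = 0.46, so a null 95% interval runs from about 0.40 to 2.5. An OR of 0.94 is a shift of about 0.15 SE, and 0.87 about 0.3 SE. In the competing-hazards model at 20% to 30% risk, two-sided type I error is about 0.052–0.053 at 20% vs 10% dropout and 0.058–0.063 at 25% vs 5%.

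**The case against.** A reader might infer that the SAP miscounts early withdrawers. The text does not go that far: it states no coding. One defensible reading of as-observed data, coding C, is unbiased under the assumptions used here. What stands is that the SAP does not choose that reading, and the borrowed analysis set, which needs only one post-baseline value, points more naturally to coding A.

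A reader might also infer that logistic regression is simply the wrong model. Protocol Section 3 and SAP 2.1 define the endpoint as a proportion, and logistic regression is a conventional model for one. This stands against discarding it, but not against estimating the same proportion by Kaplan-Meier.

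The design limits the damage. Protocol 7.1 keeps subjects in the study after they stop investigational product. Concomitant medication and exacerbations are reviewed at the Early Withdrawal visit, and Protocol Appendix 11 asks sites to collect concomitant medications when pandemic-related visits are missed. Only true study withdrawal truncates observation, but the plan itself allows for 15% dropout.

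The Cox and rate analyses of exacerbation offer a cross-check, since antibiotic treatment is one component of that definition. They cover a wider composite and do not answer the antibiotic-specific objective.

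Finally, censoring assumes non-informative withdrawal. Protocol 7.2 lists lack of efficacy, adverse event and physician decision among the reasons for withdrawal, and each could be linked to worsening CRS. This stands as a limit on the remedy.

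**Conclusion.** The gap is real and small. The plan analyses a cumulative event without allowing for incomplete follow-up and leaves the coding of event-free withdrawers unstated. Under the most natural coding, and with assumed risk and non-informative dropout, a true 25% is reported as about 23% in both arms at 15% dropout.

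Bias between arms requires unequal withdrawal, and the documents give no per-arm rates. It would be tempting to conclude that the arm losing more subjects will look protected. The documents do not support that: the direction depends on the unstated coding, and at 50 per arm the shifts are well inside sampling error unless withdrawal is very unequal, very early or related to worsening disease. The endpoint is exploratory, and no sample size rests on it. This is a cheap improvement, nice to have.

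**What to change.** In SAP 8.3.3.4 and Table 1:

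- Define time from first dose to the start of the first antibiotic course for worsening CRS. Use data through Week 16 and censor event-free subjects at the last CRS exacerbation assessment, as in 8.3.2.2.
- Report the Kaplan-Meier estimate of the Week 16 proportion in each arm with a 95% CI. This keeps the protocol's endpoint as a proportion.
- Add a Cox comparison with treatment group, disease-status stratum and region as covariates.
- Keep the logistic model as a sensitivity analysis, and state in one sentence how it codes subjects who withdraw before Week 16 without antibiotics.

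The cost is SAP wording and one more run of a model already required for 8.3.2.2. Protocol 6.5 already has start dates and reasons for use of medications recorded. There are two downsides. The model-based effect becomes a hazard ratio instead of an odds ratio. The method also assumes that withdrawal is non-informative given the covariates, so it does not cure withdrawal driven by worsening CRS, and the SAP should say so.
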